#### Treatment time and body size

We will employ the clustered-trial design in the proposed TiME trial to examine the effect of increasing dialysis session duration on mortality. In this design, the prescription of dialysis session durations based on randomization assignment of the dialysis facility will be applied to all patients initiating dialysis in that facility. However, because large patients typically receive dialysis sessions of at least 4 hours, and thus little difference in treatment time can be expected between the Intervention and Usual Care groups among such patients, the *primary analysis* will estimate the effectiveness of longer dialysis time among small and average-size patients, i.e., those with a body water volume (estimated from age, height, weight and sex) of less than or equal to 42.5 Liters. Current data from the USRDS indicate that nearly 70% of incident patients in the US, including almost all women and close to 50% of men, have body water volume less than 42.5 Liters, [personal communication, [name], USRDS Coordinating Center]. Any observed differences in outcomes between treatment groups among the larger patients will also be of interest because they will likely reflect indirect effects possibly at the dialysis facility level related to trial participation. Regardless, this design incorporates the advantages of both feasibility of trial implementation and generalizability of the results.

#### Why women and smaller patients often have shorter treatment times

Several decades ago, the usual hemodialysis treatment regimen was 6 8-hour sessions three times per week. As dialyzers became more efficient, and as determination of dialysis adequacy focused on urea reduction, a small readily-dialyzable solute, it became possible to achieve high degrees of urea removal during much shorter treatment periods, e.g., 2.5-4 hours. Current U.S. clinical practice guidelines define minimally adequate dialysis for a 3 times per week schedule as a treatment that achieves a urea reduction ratio or Kt/V of at least 65% or 1.2, respectively. A minimum treatment duration of 3 hours is recommended, but not

mandated. Because smaller individuals and those with lower muscle mass (and thus smaller total water volume) can achieve a given urea reduction ratio in less time than larger, more muscular individuals, in the United States today, many smaller patients, including most women, have treatment times shorter than 4 hours, often in the range of 3.0 - 3.5 hours or less. These treatments usually meet the guideline target of a URR  $\geq$ 65%, or Kt/V  $\geq$ 1.2 but do not take into account removal of fluid and uremic toxins with larger molecular weights and may be suboptimal in terms of survival and quality of life.

#### HEMO Study results: treatment time, women, and body size

The only recent, large randomized trial of hemodialysis therapy, the HEMO study, compared dialytic URRs of approximately 65% and 75% and found no overall benefit in terms of survival or hospitalization in the higher URR group. The increase in URR in the higher-dose group was achieved by increasing dialysis efficiency through use of higher dialyzer blood flow rates and larger dialyzers, while limiting dialysis time to the minimum. Therefore, the trial was truly a test of urea removal, but not dialysis session time or larger-molecule removal. Nonetheless, the higher-URR group required an average of 30 minutes more than the lower-URR group in order to achieve its URR target. When the HEMO study results were analyzed using an intent-to-treat comparison for women and men separately, the higher dialysis URR (and the accompanying longer time) showed a beneficial effect on all-cause mortality. Among the female participants, those assigned to the high URR group had a mean dialysis session duration of 3.5 hours compared with 3.0 hours in the controls. When results were analyzed according to body size (as estimated body water), smaller patients also seemed to benefit from assignment to the higher URR (and treatment time).

#### Survival of women and smaller patients with ESRD

The survival advantage of females seen in the general population is completely lost among patients treated with maintenance hemodialysis, as men and women have similar mortality rates. Furthermore, regardless of sex, smaller patients, defined by low estimated body water volume, have a markedly lower survival than their larger counterparts. Reasons for this are likely multifactorial, but part of the reason may be the shorter dialysis times typically prescribed for smaller patients.

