One analytical problem in assessing the relationship between dialysis dose (URR) and mortality in observational studies is that the magnitude of the dose effect far exceeds the maximum likely effect calculated from the randomized comparison in the HEMO study, the largest randomized trial conducted thus far evaluating dialysis treatment approaches (N=1,846). Thus, even though some observational studies suggest a strong benefit of increased dialysis session lengths, the apparent advantages may be overestimated due to a dose-targeting bias that is difficult to remove even with statistical adjustment for measured factors related to the patient's health status. In an analysis of CMS ESRD Clinical Performance Measures Project data that incorporated adjustment for anthropometric volume of distribution for urea, a benefit of longer time was not evident and there was a non-statistically significant trend toward worse outcomes with longer treatment times, a finding attributed by the authors to confounding by indication. Thus, a beneficial effect of increasing dialysis session duration in the routine thrice-weekly hemodialysis schedule is not definite and requires a well-powered randomized trial to confirm or refute.

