# 6. Sample Size and Analysis Plan

#### 6.1. Analysis Population

In current practice dialysis prescriptions are typically written to target urea removal. For this reason there is usually a strong association between prescribed dialysis time and estimated urea distribution volume or total body water volume (V) which usually averages 50% in women

Estimated body water	Median Treatment						
volume V(L)	Time (min)						
< 27.5	185						
27.5-32.5	206						
32.5-37.5	211						
37.5-40	213						
40-42.5	224						
> 42.5	235						

Table 1.	Treatment time and body	v water volume
		,

and 60% in men. A detailed analysis of 2,922 patients on dialysis  $\leq$ 3 years in the Renal Research Institute database in January 2012, demonstrates the expected association between treatment time and V (**Table 1**). Thus, one can foresee that for most patients with V >42.5 L, the prescribed dialysis times will be close to 4 hours, even when such

patients are receiving their initial prescriptions in a Usual Care rather than Intervention dialysis unit. Hence, for such larger patients, the times prescribed in intervention units are not expected to differ importantly

from controls.

Analysis of the same Renal Research Institute data sample suggests that about 35% of enrolling patients will have V values greater than 42.5 L and thus unlikely to be meaningfully participating

in the "time" prolongation intervention. Accordingly, the direct effects of the TiME Trial intervention will be evaluated in the *Primary Treatment Assessment Population*, which will consist of those patients with V (estimated from sex, age, and entry weight and height) ≤42.5 L.

In addition to the direct effects of treatment time, indirect effects of being enrolled in an Intervention facility versus a Usual Care facility are also possible. For example, assignment of a given dialysis facility to the Intervention group may lead to changes in unit practices that are unrelated to dialysis time but that may still affect patient outcomes. The *Extended Population* will consist of all patients in the trial and will be used to evaluate the combined direct and indirect effects of the cluster-administered intervention.

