#### 4.3 Primary Efficacy Analysis

The primary outcome is time to death and the primary efficacy analyses will be an intention-to-treat (ITT) analysis on mortality for the primary analysis population, referred to as "Watson ≤ 42.5L". Each participant will be included in the arm in which her/his dialysis facility was randomized, regardless of adherence to the assigned strategy. The analysis will be performed using Cox proportional hazards models to compare the hazard rates between the Intervention and Usual Care arms. Intra-cluster correlation (ICC) between participants within the same facility will be modeled by using a random component for the hazard function (i.e. frailty models). The hazard ratio (HR) for mortality between Intervention and Usual Care arms will be reported by calculating the exponential function of the estimated parameter of the treatment effect from the Cox models. The test statistic will be calculated to test the null hypothesis that the hazard ratio equals 1 versus the 2-sided alternative hypothesis that the hazard ratio is greater than and/or less than 1. To examine the proportionality between the Intervention group and the Usual Care group, an interaction term between treatment and a function of time will be included in the model; i.e., to determine whether the treatment effect on mortality varies as a function of time that a participant has been under the treatment. The same approach will be used for the primary outcome analysis for the extended analysis population (all participants regardless of Watson V) as well as in the stratified analyses and the large-size subgroup of participants, referred to as "Watson >42.5L".

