#### 4.4.2 Exploratory As-Treated Analyses

#### 4.4.2.1 Rationale

Non-adherence to the trial intervention is one of the most common factors complicating the application of causal inference to results from randomized trials. This is particularly the case for pragmatic trials, where the biological effect of the treatment received may differ greatly from the effectiveness of the intervention as estimated using intent-to-treat analyses. While the primary analyses will be performed using standard intent-to-treat approaches to estimate effectiveness, additional explanatory analyses using modern methods of causal inference will be performed to assess the biological effect of the treatment received; i.e., as-treated analyses.

Non-adherence to the TiME trial intervention may occur as a result of unwillingness by patients to undergo longer dialysis sessions, preference of the treating nephrologist to prescribe shorter sessions for specific patients, operational barriers for facilities, and patient transfer to non-participating facilities. Adherence information for participants will be collected during the entire follow-up period in the form of the both prescribed and delivered duration of each dialysis session and relevant timeupdated covariates.

To monitor patient adherence, we use an aggregated metric, average session duration within each patient, as well as a graphical tool, lasagna plot, at session-level for each patient. In the as-treated analysis, we will use the previously described Cox models with frailty to investigate the effect of session duration (prescribed and delivered) on mortality rate.

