One disadvantage of the as-treated analysis for mortality is that, for example, a difference in mortality for a 30-minute increase in delivered session duration is potentially confounded by unmeasured confounders (e.g. healthier patients may be more likely than sicker patients to have longer sessions). Therefore, the difference in mortality in such an analysis infers association, but not necessarily causation; or, equivalently, it is a result from an observational study, not a randomized trial. An advantage of the TiME Trial is its randomization. Consequently, we will conduct instrumental variable (IV) analyses using the randomization assignment as an instrument. The property of the instrument (randomization) is to provide a proper way to adjust for the unmeasured confounders (e.g. indication bias), and to provide a causal interpretation of the difference in mortality for a 30-minute increase in delivered session duration among compliers (those patients who, because of the randomization, increase their dialysis session duration from x minutes to x+30 minutes). Although the strength of the instrument within an IV analysis may be determined by the separation in delivered session duration between Intervention and Usual Care arms (which will be decreased by non-adherence), this will oaffect the precision of the causal interpretation (i.e. unbiased hazard ratio).

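### The exploratory as-treated mortality model has no body-size term, so its hazard ratio for longer sessions is biased towards benefit by a confounder the trial already measures

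*Combined protocol and SAP*

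**What the plan says.** **The model.** In SAP 4.4.2.1 the plan is: "we will use the previously described Cox models with frailty to investigate the effect of session duration (prescribed and delivered) on mortality rate". The model referred to is in SAP 4.3. It has treatment arm, a facility-level random component and a treatment-by-time term to check proportionality. It names no patient characteristic. SAP 4.4.2.1 says that time-updated covariates are collected, but it does not name them or put them in the model.

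**The caveat.** SAP 4.4.2.1 warns that the as-treated difference is "potentially confounded by unmeasured confounders", with general health as the example. It says that the result shows association rather than causation, and it adds an instrumental variable (IV) analysis with randomization as the instrument.

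**Body size and session time.** Protocol 6.1 reports a strong link between prescribed time and V. The Table 1 medians are 185, 206, 211, 213, 224 and 235 minutes across six rising bands of V.

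**Body size and survival.** Protocol 1.1 (Survival of women and smaller patients with ESRD) says that smaller patients of either sex "have a markedly lower survival than their larger counterparts".

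**Availability of V.** Protocol 6.1 computes V from sex, age, and entry weight and height. The primary population is defined by it.

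**The concern.** A baseline variable that goes with both longer sessions and better survival is a confounder of the duration-mortality association. The protocol states both links, and the model as written leaves the variable out. A facility frailty cannot absorb size differences between patients in the same facility. A time-updated exposure would not remove the problem either.

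The caveat in SAP 4.4.2.1 covers only confounders that are not measured. V is measured, so this part of the bias is avoidable. What is at stake is an as-treated HR that leans towards benefit, possibly reported beside a null randomized comparison.

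**Working it through.** The plan states no figure for this analysis, so there is none to reproduce. The check asks what the stated model would return if session time had no effect on death.

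**Inputs from the documents**
- Median session time by band of V: Table 1, Protocol 6.1.
- Share with V >42.5 L: 35% (Protocol 6.1).
- Mortality 18% per year (Protocol 6.2) and loss to follow-up 10% per year (Protocol 6.2.1).
- Numbers for scaling z: 6,800 in all and 4,250 at V ≤42.5 L (Table 2R).

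**Assumptions, not in the documents**
- HR for death of 0.95, 0.90 or 0.85 per 5 L of V. This drives the size of the result.
- Representative V for the bands: 25, 30, 35, 38.75, 41.25 and 48 L, with SD 1 L within a band.
- Band shares 6, 14, 20, 12, 13 and 35%; the last is the documents' figure.
- SD of session time within a band: 25 minutes.
- Potential follow-up uniform from 1.5 to 3 years.
- 0, 30 or 60% of Intervention patients moved to at least 255 minutes.

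**Step 1: closed-form approximation with no shift in the Intervention arm.** If V alone affects death, the log HR per 30 minutes from the model without V is about (log HR per litre) × (litres of V associated with 30 minutes of session time). The second factor is 30 × Cov(V, time) / Var(time).

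- All participants: Cov = 103.3; Var = 203.0 + 25² = 828.0; 30 × 103.3/828.0 = 3.74 L per 30 minutes.
- V ≤42.5 L: Cov = 47.0; Var = 102.1 + 25² = 727.1; 30 × 47.0/727.1 = 1.94 L per 30 minutes.

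| HR per 5 L | log HR per L | HR per 30 min, all | HR per 30 min, V ≤42.5 L |
|---|---|---|---|
| 0.95 | -0.0103 | exp(-0.0384) = 0.962 | exp(-0.0199) = 0.980 |
| 0.90 | -0.0211 | exp(-0.0789) = 0.924 | exp(-0.0409) = 0.960 |
| 0.85 | -0.0325 | exp(-0.1217) = 0.885 | exp(-0.0630) = 0.939 |

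**Step 2: simulated Cox regression, all participants.** These runs had 250,000 patients, a true HR of 1.00 per 30 minutes and no frailty term; z is rescaled to 6,800.

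| HR per 5 L | Shifted to ≥255 min | HR without V | z | HR with V |
|---|---|---|---|---|
| 0.95 | 0% | 0.960 | -1.75 | 0.997 |
| 0.95 | 60% | 0.978 | -0.99 | 1.005 |
| 0.90 | 0% | 0.922 | -3.54 | 0.994 |
| 0.90 | 60% | 0.941 | -2.77 | 0.991 |
| 0.85 | 0% | 0.881 | -5.57 | 0.999 |
| 0.85 | 60% | 0.920 | -3.81 | 1.001 |

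The 0% rows agree with Step 1. Comparing by randomized arm in the same runs gave 0.99 to 1.01.

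**Step 3: V ≤42.5 L.** Table 1 medians still span 185 to 224 minutes, which is 39 minutes and more than one 30-minute unit. Smaller runs (40,000 patients before restriction) gave HRs of 0.924 to 0.988 and z of -0.44 to -2.70 at 4,250. A further rerun gave 0.94 to 0.99 and z of -0.2 to -2.3. These runs are noisier: the 0.924 compares with 0.939 in Step 1.

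**The case against.** **The analysis is already limited.** Its heading calls it exploratory, it is described as observational, and the causal question goes to the IV analysis. Body size does not confound that analysis in expectation, because the instrument is the randomized arm. All of this stands and keeps the point minor. It does not justify leaving a measured confounder out of the reported as-treated estimate.

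**Silence on covariates may be only under-specification.** The SAP may have meant a class of model. Protocol 6.3 does plan marginal structural and structural nested models, and SAP 4.4.2.1 mentions causal methods generally. But its as-treated paragraph names neither of those models, and the only Cox model described earlier has no patient covariates. Where the SAP intends a multivariable Cox model, as for first hospitalization in SAP 4.5.1, it says so. The covariate adjustment in Protocol 6.3 is for imbalance between arms. V should be balanced between arms even though it is unbalanced across session times.

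**The size is assumed.** This stands. Moving Intervention patients to 255 minutes weakens the link between V and duration, and restricting to V ≤42.5 L shrinks the bias further. Protocol 1.1 also suggests that shorter sessions may explain part of the survival gap, so the whole gradient need not be confounding.

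**A stronger reading of the background.** A reader might infer that the protocol has already shown volume adjustment removing a time benefit, because it cites an analysis that "incorporated adjustment for anthropometric volume of distribution for urea, a benefit of longer time was not evident". That passage gives no unadjusted result for comparison. It reports a non-significant trend towards worse outcomes with longer time, which that study's authors put down to confounding by indication. The protocol's stated worry there is dose-targeting bias, not body size. One of the two provider-database studies it cites reports, in its title, an association independent of body weight. The background therefore does not establish that size explains the association.

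**V is not the only omitted factor.** This also stands. V adjustment returns the HR to 1 in the simulation because V is the only confounder there. Age, comorbidity and catheter use are collected too and are also absent from the model.

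**Conclusion.** The point holds as a minor one. As written, the as-treated Cox estimate is biased towards benefit by body size. The direction follows from the protocol's own two statements; the size does not.

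Under assumed gradients of HR 0.85 to 0.95 per 5 L and 0 to 60% of Intervention patients moved to 255 minutes, a null effect would appear as an HR per 30 minutes of about 0.88 to 0.98 in all participants, with z from about -1 to -5. At V ≤42.5 L it would appear as about 0.92 to 0.99, with z mostly between -0.2 and -2.7. The SAP does not say which population this analysis uses.

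A reader might infer that a highly significant false benefit is to be expected. That needs a steep gradient, which the documents do not give, and the use of all participants. Nor should these HRs be set against the design HR of 0.85, which compares arms and is not a per-30-minute effect. The intention-to-treat and IV results are not affected, and no confirmatory conclusion depends on this model.

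**What to change.** In SAP 4.4.2.1:
- Adjust every as-treated Cox model of prescribed or delivered duration for baseline V (continuous, as a spline) and sex, together with the other baseline prognostic factors already collected: age, comorbidity and catheter use.
- State the analysis population or populations.
- Report the adjusted HR per 30 minutes as the as-treated result, still labelled as association, since confounding by health status may remain.
- Extend the caveat so that it separates measured confounders, which are adjusted for, from unmeasured ones.

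This takes a few sentences in the SAP and no new data. The cost is a somewhat wider interval for session duration, because V and duration are correlated (about 0.48 in all participants with no shift, under the assumptions above). V precedes session time, so adjusting for it does not remove a true effect of duration.

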#### Safety of the TiME Trial intervention

The dialysis session duration being evaluated in the TiME Trial is well within the range of session durations administered in routine clinical practice. While there have not been clinical trials designed specifically to evaluate the safety of treatment sessions of 4 - 4.5 hours, there is not a theoretical basis for concern about reduced safety with 4.25-hour sessions compared with shorter sessions, nor have such concerns arisen from observational studies, including studies of treatments of 6 - 8 hours. Dialysis sessions that are of longer duration are expected to generate less hemodynamic stress than shorter treatments because of slower

removal of fluid. Serious complications of hemodialysis related to technical aspects of the dialysis procedure such as air embolism and hemolysis are extremely rare, typically occur within the first 10-60 minutes of a dialysis session, and are not related to dialysis session duration.

#### Summary of rationale for the TiME Trial intervention

There is considerable skepticism about whether urea-based determination of dialysis adequacy (i.e., URR or Kt/V) provides a sufficient approach to prescribing hemodialysis session duration, although this is the current practice standard in the United States. Physiological considerations and observational data provide a rationale for session durations that are longer than many patients currently receive. Daily hemodialysis appears to confer benefits with respect to several important surrogate outcomes; however, patient acceptance of frequent therapies is not very high, even in a highly selected and motivated sub-population. Additionally, there are operational barriers to instituting more frequent therapy, such that 97% of hemodialysis treatments in the United States are administered on a thrice-weekly schedule. Given this reality, optimizing the prescription parameters for a thrice-weekly schedule has the potential of providing benefits to a large proportion of patients. Moreover, if women and small patients are receiving inadequate dialysis it is critical to address this. Although several thought leaders in dialysis care have proposed broad implementation of longer dialysis sessions, there is enough uncertainty about the benefits of longer treatment times that evaluation through an adequately-powered randomized trial is warranted before widespread changes in practice are recommended.

